distress and to develop better, individually targeted interventions. Recent work in our laboratory has identified one such phenotype, Excessive Self-Consciousness (ESC), that cuts across depression and anxiety disorder presentations, predicts specific impairments in real-world interpersonal functioning, and correlates with a particular pattern of dysfunction in neural systems. In this study, we propose to test whether the ESC phenotype can be used to guide a novel, transcranial direct current stimulation (tDCS) intervention to target specific abnormalities in cortical network functioning.

ESC has long been recognized as one component of the general trait-like disposition to experience negative emotions. It describes the tendency to feel shame, humiliation, and inadequacy around others. In our work with depressed adults, we observed that higher levels of ESC were associated with the following neurofunctional abnormalities during emotion regulation: 1) inefficient functioning of the top-down, cognitive control network necessary to regulate negative emotions; 2) abnormally increased activity in regions of the parietal cortex that are typically active during self-reflection; and 3) a pattern of network interference by which the elevated activity in the parietal regions interfered with communication in the cognitive control network.

In this study, we propose to test whether the ESC dimensional phenotype can be used to guide a novel tDCS intervention to target the network-based abnormalities described above. tDCS involves passing a weak current through the brain. One variant, cathodal tDCS, can be used to temporarily hyperpolarize cortical pyramidal cells, thereby decreasing neuronal connections. tDCS has been explored as a possible treatment for depression, but results to date are mixed. No work has examined whether tDCS can be used in an individually guided manner to target locations in the parietal cortex and alter the patterns of circuitry dysfunction described above. The aims of this study were designed to provide pilot data for a competitive future funding proposal:

1) Determine the impact of acute cathodal tDCS to regions of the left posterior parietal cortex associated with self-reflection on the patterns of abnormal neural activity and connectivity described above. We will compare this to a sham condition whereby no active tDCS will be applied.

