2) Determine if the impact of the intervention is greater for those with higher vs. lower levels of ESC, controlling for symptoms of depression and anxiety.

3) Document the feasibility and acceptability of the intervention, and explore whether the tolerability or efficacy of the intervention differs as a function of demographic variables or psychiatric symptoms.

Study Design & Methods

Sample: In order to demonstrate that the patterns of functional neural abnormalities associated with ESC can be specifically altered by cathodal tDCS, we will recruit a sample of 44 adults (18-30 years old, 50% male/female), all of whom will have clinically significant levels of depression (≥ 10 on the Quick Inventory of Depressive Symptoms^{29,30}) or anxiety (≥ 60 on the PROMIS Anxiety Short-form³¹). We are selecting a sample of depressed and anxious adults so that we can confirm that it is the ESC dimensional phenotype, and not psychiatric symptom severity, that is associated with the patterns of cortical functioning abnormalities described above. To ensure an adequate range of ESC scores, the sample will be stratified to require that half (N=22) fall in the upper tertile of ESC scores expected among adults with depression or anxiety² and half (n=22) fall in the bottom tertile.

Procedures: The proposed study will be carried out at the University of Pittsburgh, Magnetic Resonance Research Center (MRRC). Participation will occur over three assessment periods. If participants appear eligible after a telephone screen, they will be scheduled for Visit 1 (which may be virtual or in-person), during which a more thorough set of screening procedures will

determine full eligibility and demographic, symptom, trait, functioning, and life history information will be collected. If participants continue to be eligible following Visit 1, they will be scheduled for two scan visits (Visits 2 and 3) to be held on separate days, approximately one week apart. The following data will be collected:

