fMRI Protocol (Visits 2 and 3): At each scanning visit, symptoms (i.e., QIDS, PROMIS-A) will be reassessed. During fMRI at each visit, participants will complete the Cognitive Reappraisal Task. This widely used task examines the functioning of the neural circuitry associated with exerting cognitive control over the response to emotionally salient stimuli.^{34,35} Each trial begins with an instruction cue (2s) to either “attend” or “reappraise” the image that will follow. Next, a negatively or neutrally valenced interpersonally relevant picture is presented (8s) during which participants follow the instructions given for that trial. The task consists of three trial types: attend neutral, attend negative, and reappraise negative. During attend trials, participants view the scene and experience their natural emotional response. During the reappraise trials, participants are asked to reframe the meaning of the scene so as to diminish the negative emotional impact.³⁶ Participants practice the task prior to the scan, and they are provided feedback on their reappraisals of practice items. The stimulus display is followed by an emotional rating probe (4s) and finally a fixation cross (4s) to mark the end of the trial. Twenty trials of each type are presented in a pseudorandom order over two 10 minute, 20 second runs. Two versions of the task have been developed to facilitate repeated testing. These will be counterbalanced across subjects and visits. This task has been used in several studies of healthy adults,³⁷⁻³⁹ and [name] has successfully used the task in a sample of depressed individuals. Prior to fMRI scanning, structural brain data will be collected for all participants. Following the final visit, participants will complete a short, self-report questionnaire regarding their experience of the intervention and will be debriefed by study personnel.

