tDCS Protocol (Visits 2 and 3): TDCS will be administered concurrently with the emotion regulation paradigm in the scanner using procedures already in place at the MRRC. TDCS is applied to the scalp, typically providing the equivalent of what a 6V battery would produce (and providing no more than 15V). The TDCS sponge electrodes and connecting wires are non-ferromagnetic and thus can be used safely within the MRI facility. These will be connected to the main apparatus situated outside of the facility. Investigators have determined the optimal placement of wires in the scanning environment to reduce occurrence of scanning artifacts. The montage for left posterior parietal cortex stimulation and the sham will be based on our prior work, the published literature²⁶, and neurotargeting software. We will employ left posterior parietal cortex cathodal stimulation and anodal stimulation on the shoulder. Cathodal stimulation of -1mA will be used, as this produces neural inhibition⁴¹, and because higher cathodal stimulation currents can yield paradoxical excitation⁴². Voltage is controlled by the device to maintain a constant electrode -1mA current. Cathodal stimulation will be applied for the duration of the emotion regulation task (approx. 20 minutes), and it will be slowly ramped up to start and ramped down to end. Previous findings indicate that effects of acute TDCS can last about 2 hours after the procedure but not into the next day⁴². Side effects: mild skin sensations under

the electrode (itching, prickling), dizziness, visual flickering; much less frequently, nausea, headache and more serious atopic skin reactions. There is a built-in safety mechanism to prevent shorting and discomfort. Participants indicate, using a squeeze ball, if they feel scalp warmth. Sham stimulation will be slowly ramped up and down to a nominal low level (1ua).

Eligibility Criteria

Inclusion Criteria:

- 1) Between 18-30years old
- 2) Score > 10 on the QIDS or > 60 on the PROMIS-A
- 3) We will use a flexible extreme groups recruitment strategy to ensure an adequate distribution of ESC scores. We will ensure that at least 62% of the sample will be composed of those scoring .5 SD above or below the mean, as measured by the NEO-PI-R. This value corresponds to the expected values assuming a normal distribution of the trait.
- 4) Normal or corrected to normal vision
- 5) Able to provide informed consent in English
- 6) Right-handed (Annett criteria)

Exclusion Criteria:

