- 1) Have a history of head trauma with loss of consciousness.
- 2) Have a systemic medical illness that may impact fMRI measures of cerebral blood flow.
- 3) Meet standard exclusion criteria for fMRI scanning (e.g. claustrophobia, cardiac pacemakers, neural pacemakers, surgically implanted metal devices, cochlear implants, metal braces, or other MRI non-safe metal objects in the body).
- 4) Are pregnant (self-report and tested for as part of any scan by the scanning center)
- 5) Not native English speaking or not fluent
- 6) Premorbid NAART IQ estimate<85;
- 7) Visual disturbance (<20/40 Snellen visual acuity) with correction
- 8) Left/mixed handedness (Annett criteria), to ensure a uniform hemispheric dominance for interpretation of neuroimaging data
- 9) Active suicidal ideation in need of immediate treatment
- 10) Scoring below the cutoffs on both the QIDS and the PROMIS-A
- 11) History of alcohol/substance use disorder (including nicotine) and/or illicit substance use (except cannabis) over the last 3 months, determined by the MINI. Lifetime/present cannabis use (non-disordered levels) will be allowed, given its common usage in individuals in this age range.
- 13) Current or past psychotic-spectrum disorder
- 14) History of seizures

Statistical Considerations

A1: Repeated-measures ANOVA models will be used to determine whether acute cathodal tDCS to the left posterior parietal cortex, compared to the sham condition, alters patterns of neural activity in and connectivity with the posterior parietal cortex and corresponding patterns of activity and connectivity within the cognitive control network during emotion regulation. A2: Repeated measures ANCOVA models will determine whether the impact of tDCS is stronger for those with higher ESC scores, controlling for concurrent depression and anxiety symptoms. A3: Feasibility and tolerability of the intervention will be assessed by examining attrition rates between the fMRI/tDCS visits and by examining responses on the self-report questionnaire regarding the acceptability of the intervention. Differences in acceptance, tolerability, and efficacy will be explored as a function of demographic variables and psychiatric symptoms.

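### Active/sham order across Visits 2 and 3 is not stated and A1/A2 name no visit term, so confounding of tDCS with visit cannot be excluded from the text; randomise a balanced order and add visit to both models

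*Combined protocol and SAP*

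**What the plan says.** Aim 1 (Study Objectives) sets active cathodal tDCS against sham: "We will compare this to a sham condition whereby no active tDCS will be applied". The Procedures paragraph schedules "two scan visits (Visits 2 and 3) to be held on separate days, approximately one week apart", and the tDCS Protocol is headed for both visits. Together with the repeated-measures analysis and the remark on how long tDCS effects last, this reads as a within-person comparison with one condition at each visit. That is an inference; no sentence says so outright.

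On order, the one relevant statement is in the fMRI Protocol: "Two versions of the task have been developed to facilitate repeated testing. These will be counterbalanced across subjects and visits". It concerns the two versions of the reappraisal task, not active and sham. On carry-over, the tDCS Protocol says: "Previous findings indicate that effects of acute TDCS can last about 2 hours after the procedure but not into the next day".

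In the Statistical Considerations, A1 reads "Repeated-measures ANOVA models will be used to determine whether acute cathodal tDCS to the left posterior parietal cortex, compared to the sham condition", followed by the neural outcomes. A2 says "ANCOVA models will determine whether the impact of tDCS is stronger for those with higher ESC scores, controlling for concurrent depression and anxiety symptoms". Visit, order and task version appear in neither.

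Two rules govern the spread of ESC. Under Sample, "the sample will be stratified to require that half (N=22) fall in the upper tertile of ESC scores", with the other half in the bottom tertile. Inclusion criterion 3 instead says "We will ensure that at least 62% of the sample will be composed of those scoring .5 SD above or below the mean".

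**The concern.** A second scan can differ from the first for reasons unrelated to stimulation, such as practice at reappraisal or getting used to the pictures and the scanner. Having two task versions and practice before the scan may reduce such a visit effect, but does not take it out of the comparison. Counterbalancing versions does not balance active and sham over visits either.

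What happens to the visit effect depends on the order of conditions, which the protocol leaves open. With balanced order it goes into the error term. With uneven order, part of it enters the tDCS estimate. With one fixed order, all of it does. If order is related to ESC, the tDCS-by-ESC estimate in A2 moves in the same way.

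These pilot estimates are meant to support a later funding proposal, so readers will want to separate tDCS from repeat scanning. Order cannot be repaired once scanning is done.

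**Working it through.** **Inputs from the protocol.** N = 44 (Sample); two scan visits (Procedures). The protocol gives no power, alpha, effect size, SD or visit effect, so there is no figure to reproduce.

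**Assumptions.** Two-sided 5% test; all 44 complete; each outcome reduced to one within-person difference with residual SD 1; visit effect δ (Visit 3 minus Visit 2) between 0.1 and 0.75 of that SD, with 0.25 used in step 2. The benchmark tDCS effect is 0.432 SD, which has 80% power in a paired test at N = 44.

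**Model.** Dᵢ = active − sham = τ + sᵢδ + eᵢ, with sᵢ = +1 if active is at Visit 3 and −1 if at Visit 2. A1 as written tests the mean of D. A visit term adds sᵢ to the model.

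**Step 1: balanced order, 22/22.** The sᵢ sum to zero, so there is no bias. Without visit, the SE is about √(1 + δ²)/√44. At δ = 0.5 this is 1.118 × 0.1508 = 0.169 (simulated mean 0.168). With visit it is 0.5 × √(1/22 + 1/22) = 0.151 (simulated mean 0.150), whatever δ is. Simulation, 200,000 runs per cell:

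| δ (SD) | Power, visit omitted | Type I error, visit omitted |
|---|---|---|
| 0.1 | 80% | 4.9% |
| 0.2 | 79% | 4.6% |
| 0.3 | 77% | 4.1% |
| 0.5 | 73% | 2.9% |
| 0.75 | 63% | 1.4% |

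With visit and task version both in the model, power is 80% and type I error 5.0% throughout. With visit alone (42 error df), the noncentral t gives 79.96%.

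**Step 2: uneven order, visit omitted.** Shift of the estimate = δ(n₁ − n₂)/44. Type I error from 20,000 runs per cell:

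| Split | (n₁ − n₂)/44 | Shift at δ = 0.25 | Type I error | Shift at δ = 0.5 | Type I error |
|---|---|---|---|---|---|
| 26/18 | 0.182 | 0.045 | 5.2% | 0.091 | 5.6% |
| 30/14 | 0.364 | 0.091 | 7.9% | 0.182 | 16% |
| 44/0 | 1.000 | 0.25 | 37% | 0.50 | 90% |

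With a visit term, type I error at 30/14 is back to 5%, with SE 0.161 and power about 75%. At 44/0 every sᵢ is the same, only the sum τ + δ can be estimated, and a visit term does nothing. At δ = 0.2 the 44/0 type I error is already about 26%.

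**Step 3: order by coin flip.** The chance of a 26/18 split or worse is 0.291 (binomial, 44, 0.5). Averaged over all splits, type I error is 5.0 to 5.1%. Power without visit is 78%, 71% and 61% at δ = 0.2, 0.5 and 0.75, against 79% with it.

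**Step 4: Aim 2, illustrative.** Dᵢ = τ + β·ESCᵢ + sᵢδ + eᵢ, with order 22/22 overall but not balanced on ESC, the same δ at every ESC level and no symptom covariates. β is set to give 80% power when δ = 0: 0.360 per ESC SD under the tertile rule, and 0.444 for a normal sample, where P(|Z| > 0.5) = 0.617 matches the 62% rule.

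| ESC recruitment, δ | Visit omitted | Visit only | Visit and visit×ESC |
|---|---|---|---|
| Tertile, 0.2 | 78.3% | 78.9% | 77.9% |
| Tertile, 0.5 | 70.1% | 78.7% | 77.7% |
| Normal, 0.2 | 78.4% | 79.0% | 77.2% |
| Normal, 0.5 | 71.1% | 79.2% | 77.4% |

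Visit alone gains 0.6 points at 0.2 SD and 8 to 9 at 0.5 SD. Adding visit×ESC gives back 1.0 point (tertile) or 1.8 (normal).

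**The case against.** The strongest reply is that a short pilot protocol need not list every model term. The sponsor may well randomise order and fit visit, and silence shows neither that order is fixed nor that the fitted ANOVA will lack the term. That stands, and it is why the point concerns what the text allows rather than what will be done.

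It is also fair that all visit-effect sizes here are assumed, that with balanced order the omission only makes the test conservative, and that at 0.2 SD or below the gain is about one point of power or less. The Aim 2 figures stand further from the plan: they leave out the symptom covariates, which are remeasured at each scan and might absorb some visit-related change. All the runs assume 44 completers. Dropout after Visit 2 could unbalance even a blocked order, which argues for the visit term rather than against it.

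A reader might infer that active and sham are in fact confounded with visit. The documents do not support that; they do not say how order is set. A reader might instead infer that lost precision is the main cost in every case. That holds only if order is close to balanced, which is the very thing left unstated. Nor is carry-over the issue: the stated duration of the effect and the gap of about a week deal with it.

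**Conclusion.** The concern holds in this form: the protocol neither states the active/sham order nor names visit in A1 or A2, so confounding with visit cannot be ruled out from the text.

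The size depends on the order used. With balanced order there is no bias; the cost is about 1, 7 and 17 points of power at assumed visit effects of 0.2, 0.5 and 0.75 SD (80% falling to 79%, 73% and 63%). With uneven order the estimate shifts by (n₁ − n₂)/44 of the visit effect, and type I error is about 16% at 30/14 and 0.5 SD. With one fixed order the whole visit effect enters the estimate and no analysis can remove it.

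Fixing the order by design is therefore the more important half of the remedy; the visit term is a cheap gain in precision and protects against chance imbalance. Confidence in the size is medium, because the SD scale, visit effects, benchmark effect and full completion are all assumptions.

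**What to change.** Before the first scan, state that active/sham order is randomised in balanced blocks crossed with task version. Balance it across ESC level too, once the tertile rule under Sample and the 62% rule in inclusion criterion 3 have been reconciled; until then the ESC strata cannot be fixed.

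Add visit as a within-person main effect in A1 and A2. In ANOVA software this can be done by entering order as a two-level between-participant factor; its interaction with condition is the visit effect. A mixed model with the same terms would also serve.

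Task version in A1 is an optional further term. Keep visit×ESC in A2 as a sensitivity analysis only, since it costs one to two points of power when the visit effect does not vary with ESC.

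The cost is one sequence list and one error df per model: A1 goes from 43 to 42 (41 with task version), and A2 from 42 to 41 before symptom covariates. No participants, visits or procedures are added.

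### A1 and A2 name repeated-measures ANOVA/ANCOVA with no rule for participants who have only one usable scan; a mixed model on all usable scans would be a cheap, modest improvement

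*Combined protocol and SAP*

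**What the plan says.** **Design.** Under Study Design & Methods (Sample), the plan states that "we will recruit a sample of 44 adults". Under Procedures, eligible participants continue: "they will be scheduled for two scan visits (Visits 2 and 3) to be held on separate days, approximately one week apart". Aim 1 under Study Objectives gives the comparator: "We will compare this to a sham condition whereby no active tDCS will be applied". The tDCS section covers both scan visits. Together with a repeated-measures model, this reads as one active and one sham visit per person. The documents do not call it a crossover, and they do not say how the order of active and sham is set. The only balancing described, in the fMRI Protocol section, concerns the two task versions: "These will be counterbalanced across subjects and visits".

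**Analysis (Statistical Considerations).** For A1 the plan states: "Repeated-measures ANOVA models will be used to determine whether acute cathodal tDCS to the left posterior parietal cortex, compared to the sham condition", changes activity and connectivity. A2: "Repeated measures ANCOVA models will determine whether the impact of tDCS is stronger for those with higher ESC scores", adjusted for concurrent depression and anxiety symptoms. A3 assesses feasibility partly by "examining attrition rates between the fMRI/tDCS visits".

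**Symptoms.** The fMRI Protocol section says: "At each scanning visit, symptoms (i.e., QIDS, PROMIS-A) will be reassessed". It does not say whether this happens before or after stimulation.

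**Not given.** There is no dropout rate, analysis set, missing-data method, rule for a participant with one usable scan, or sensitivity analysis.

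**The concern.** A repeated-measures ANOVA in its usual form needs a value in every cell of the within-person factor. If condition is that factor and each person contributes one active and one sham visit, a participant without a usable second scan has an empty cell and is removed whole, along with a complete Visit 2 scan.

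Two things could follow. Data already acquired from a 44-person pilot would go unused. And if those who leave after active stimulation differ in their Visit 2 response from those who leave after sham, the contrast among people with both scans is no longer the contrast for the recruited sample. The study is meant to supply pilot data for a funding proposal, so a shifted estimate would carry into the next design.

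**Working it through.** The plan gives no power calculation or dropout figure, so there is nothing of its own to reproduce.

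**Inputs.** From the documents: 44 participants and two scan visits. Assumed: 22 per order, outcome SD 1, true effect 0, no carry-over, between-visit correlation r of 0.3, 0.5 or 0.7, and the dropout rates below.

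**Step 1: scans discarded.** Loss of 5%, 15% or 30% of 44 removes about 2, 7 or 13 people and leaves 42, 37 or 31 pairs. The paired difference detectable with 80% power at two-sided 0.05 rises from 0.43 SD of the differences with 44 pairs to 0.44, 0.47 and 0.52.

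**Step 2: what keeping those scans recovers when loss is random.** With condition and visit terms, the full-data variance of the contrast is 2(1 - r)/44; at r = 0.5 the standard error is sqrt(1/44) = 0.151. With loss d, complete pairs keep a fraction 1 - d of the information. The one-scan records add d(1 - r)/2, because they support only a between-person comparison. The variance ratio, complete pairs to all scans, is therefore 1 + [d/(1 - d)] x (1 - r)/2. At d = 0.15, d/(1 - d) = 0.176:

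- r = 0.3: 1 + 0.176 x 0.35 = 1.06
- r = 0.5: 1 + 0.176 x 0.25 = 1.04
- r = 0.7: 1 + 0.176 x 0.15 = 1.03

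Simulation at 15% random loss gave about 3-8%, which agrees.

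**Step 3: bias when loss is not random.** Let m_A and m_S be the mean standardised Visit 2 response among those who stay after active and after sham. The expected active-minus-sham difference is (1 - r)m_A among active-first stayers and -(1 - r)m_S among sham-first stayers. Averaging the two orders, as a model with a visit term does when orders are balanced:

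bias = (1 - r)/2 x (m_A - m_S)

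This is zero when loss is random, when it depends on condition alone (both means are 0), and when it depends on response equally in both orders (the means are equal). Simulation agreed, with bias within 0.011 SD in all three cases.

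Now suppose that leaving has a latent correlation of 0.7 with the Visit 2 response. With proportion p lost, m = -0.7 x phi(z_p)/(1 - p), where phi is the normal density at the p-th quantile. The factor phi(z_p)/(1 - p) is 0.424 at p = 0.25, 0.274 at 0.15 and 0.109 at 0.05.

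- 25% versus 5%: m_A - m_S = -0.7 x (0.424 - 0.109) = -0.22. Multiplying by 0.35, 0.25 and 0.15 gives bias of -0.08, -0.06 and -0.03 SD for r = 0.3, 0.5 and 0.7.
- 15% versus 5%: -0.7 x (0.274 - 0.109) = -0.116, giving -0.04, -0.03 and -0.02 SD.

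Simulations with 44 people gave -0.08, -0.05 and -0.04 SD for the first case and -0.05, -0.03 and -0.02 SD for the second. They differ from the formula by no more than rounding and simulation error. A likelihood-based estimate on all scans stayed within about 0.01 SD of zero. The sign is negative because people with higher values are assumed to leave; it reverses if people with lower values leave.

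**The case against.** The strongest reply is that the effect is small and its premises are assumed. Nothing in the documents points to 25% leaving after active and 5% after sham. The tDCS section describes about 20 minutes of -1 mA with mostly mild sensations and no effect lasting into the next day. Even at 25% versus 5%, the bias is under half a standard error (0.08 against 0.19 at r = 0.3), and the type I error of the completers-only test was 0.067, 0.061 and 0.053 for r = 0.3, 0.5 and 0.7. This is also a pilot that claims no power. All of that stands, and it limits the point to a modest improvement.

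Three stronger readings are tempting, and the documents do not support them:

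- **That the plan expects attrition of some size.** A3 makes attrition an outcome and states no expected loss.
- **That dropout as such biases A1.** By step 3 it does so only if leaving depends on condition and response jointly. Stronger assumed dependence produced bias of up to -0.18 SD, but nothing in the documents supports that setting.
- **That ANCOVA cannot use symptoms re-measured at each visit.** Many software layouts take one covariate value per person, but a linear-model ANCOVA with participant as a factor accepts visit-varying covariates. The plan's reference to concurrent symptoms may mean exactly that.

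It is also fair to say that the unstated order of active and sham is the more basic gap. If order were fixed, condition and visit could not be separated by any model. What survives is that the plan names a method which conventionally drops one-scan participants and offers no other handling, although loss between the visits is foreseen.

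**Conclusion.** The point holds as a cheap and modest improvement to the stated analysis. Precision is a minor reason for it: random loss of 15% costs about 3-8% of variance. Protection against bias is the better reason, but it is conditional. The bias is about -0.03 to -0.08 SD at 25% versus 5% loss and about -0.02 to -0.05 SD at 15% versus 5%, only if leaving depends on both the condition and the response at Visit 2.

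These figures assume balanced order, a within-person design that is inferred, and dropout rates and correlations that the documents do not give. They concern the A1 condition contrast; the ESC-by-condition term in A2 was not quantified. A reader might infer that the A1 estimate will be wrong as planned. The documents do not support that: with complete pairs, or with loss unrelated to condition and response jointly, it is unbiased.

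**What to change.** In Statistical Considerations, for the same outcomes and contrasts, replace the repeated-measures ANOVA/ANCOVA with a linear mixed model that has a random participant intercept and fixed condition and visit. For A2, add ESC and ESC-by-condition. Include every participant with at least one usable scan, and report the both-visits analysis as a sensitivity check.

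Two conditions need to be written alongside it:

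- State how the order of active and sham is assigned. The visit term can be fitted only if that order varies across participants.
- State when QIDS and PROMIS-A are completed at each scan visit. Enter their visit-specific values in A2 only if they are measured before stimulation at that visit; otherwise the adjustment could remove part of the effect.

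**Cost.** A few sentences and a different model specification, with no extra data or participants. The documents do not say whether outcomes are regional or voxelwise, so the programming effort cannot be judged exactly. With complete data and balanced order, the A1 condition test matches a visit-adjusted paired analysis. The downside is that one-scan participants enter under a missing-at-random assumption: leaving may depend on what was observed at Visit 2 but not on the unseen second scan. The precision gain is modest.

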Study Protocol

Official Title: Modulating Default Mode Function: A Transcranial Direct Current Stimulation (TDCS) Pilot Study

ClinicalTrials.gov ID (NCT number): NCT04598152

Protocol Date: 11/24/2020

Scientific Background

Several theories about depression and anxiety suggest that a broad dimension of negative affectivity is shared by the disorders.^{1,3,10,11,15} This dimension represents the tendency to experience negative emotions and to cope inadequately with emotional distress.¹⁶ Recent work in our laboratory has begun to identify and describe one specific component of the broad dimension of negative affectivity, Excessive Self-Consciousness (ESC), that holds promise as a specific phenotype underlying depression and anxiety in adults. This dimension reflects the tendency to feel shame, embarrassment, humiliation, and inadequacy around others.

Preliminary work suggests that it is uniquely associated with impairments in interpersonal functioning over and above psychiatric symptoms, and it is associated with a specific pattern of disruption in the functioning of neural systems during emotional regulation. Specifically, among adults with depression, we have observed that higher levels of ESC are associated with: 1) decreased top-down control from the dorso- and ventrolateral prefrontal cortex (DLPFC, VLPFC; portions of the cognitive control network)^{17,18} during regulation of an initial emotional response in the amygdala; 2) heightened activity during emotion regulation in the precuneus and posterior parietal cortex, regions typically active when thinking about on oneself,¹⁹⁻²¹ and 3) an abnormal pattern of interference by which the abnormally elevated activity in parietal regions alters the patterns of connectivity in the cognitive control network – specifically, decreasing the communication between the DLPFC and the dorsal Anterior Cingulate Cortex (ACC), a region critical for the adaptive regulation of emotional experience.^{17,22} The goal of the proposed project is to determine whether direct, temporary hyperpolarization of portions of the posterior parietal cortex associated with self-referential processing can alter the patterns of abnormal functioning described above and provide a more effective and targeted treatment option for individuals with high levels of ESC, regardless of diagnosis.

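### Does A2's control for depression and anxiety symptoms leave the tDCS-by-ESC test unadjusted for symptom severity?

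*Combined protocol and SAP*

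**What the plan says.** A2 is one sentence. It names repeated-measures ANCOVA and asks whether the tDCS effect "is stronger for those with higher ESC scores, controlling for concurrent depression and anxiety symptoms". Aim 2 in Study Objectives asks whether the effect is "greater for those with higher vs. lower levels of ESC, controlling for symptoms of depression and anxiety". Neither place lists the model terms.

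Four other places bear on the point:

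- The Sample paragraph gives the reason for recruiting depressed and anxious adults: to confirm that "it is the ESC dimensional phenotype, and not psychiatric symptom severity, that is associated with the patterns of cortical functioning abnormalities".
- The fMRI Protocol says: "At each scanning visit, symptoms (i.e., QIDS, PROMIS-A) will be reassessed". Each person therefore has two scan-visit scores per scale. ESC comes from the NEO-PI-R at Visit 1 and is fixed within person.
- A3 adds that "efficacy will be explored as a function of demographic variables and psychiatric symptoms".
- Exclusion criterion 10 reads "Scoring below the cutoffs on both the QIDS and the PROMIS-A", so a high score on either scale is enough to enter.

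That each participant has one active and one sham visit is implied by the two tDCS scan visits, the sham comparison and the repeated-measures models. It is not stated outright.

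**The concern.** In a within-person comparison, adding a covariate to the model is not the same as adjusting the treatment contrast for it. A symptom score that is the same at both visits affects both conditions equally and drops out of their difference. An analyst could therefore include QIDS and PROMIS-A, report that symptoms were controlled for, and leave the tDCS-by-ESC estimate where it was.

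Separating ESC from severity is central to the study. The Scientific Background describes ESC as "one specific component of the broad dimension of negative affectivity", a dimension it says depression and anxiety share, so some correlation between ESC and symptoms is plausible. A3 allows that efficacy may vary with symptoms. If both hold and symptoms enter as main effects only, severity moderation could be reported as ESC moderation. The result would be carried forward, since the Study Objectives say: "The aims of this study were designed to provide pilot data for a competitive future funding proposal".

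**Working it through.** The documents give no alpha, effect size or power figure for A2, so there is no stated figure to reproduce. The check is algebra, then simulation under labelled assumptions.

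**Algebra.** Let c = 1 for active and 0 for sham, and let S be a symptom score:

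Y(i,c) = u(i) + b1·c + b2·ESC(i) + b3·c·ESC(i) + g1·S(i,c) + g2·c·S(i) + error

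Active minus sham gives:

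D(i) = b1 + b3·ESC(i) + g1·[S(i,1) − S(i,0)] + g2·S(i) + error

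- Main effects only (g2 left out), stable S: the g1 term is zero, so b3 is exactly the unadjusted slope.
- Main effects only, visit-specific S: only the between-visit change is adjusted for, not severity.
- Crossed with condition (g2 kept): b3 is adjusted for severity.

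If g2 is left out when it is not zero, the ESC slope is biased by g2 × (slope of S on ESC).

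**One simulated data set.** N = 44, outer-tertile ESC, ESC-symptom correlation 0.5, true ESC slope 0.3, true slope on the symptom mean 0.3. The expected unadjusted slope is 0.3 + 0.3 × 0.5 = 0.45.

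| Symptom terms | tDCS-by-ESC estimate (SE) |
|---|---|
| None | 0.449 (0.150) |
| Stable score, main effects | 0.449 (0.150) |
| Visit scores, main effects | 0.425 (0.151) |
| Stable score, crossed with condition | 0.198 (0.221) |
| Visit scores, crossed with condition | 0.212 (0.203) |

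The first two rows agree to five decimals, as the algebra requires.

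**Repeated trials, symptoms the only true moderator.** 4,000 trials per setting, slope 0.6 on the symptom mean, no eligibility cut, correlations 0.3/0.5/0.6. Expected bias is 0.6 × 0.3 = 0.18, 0.6 × 0.5 = 0.30 and 0.6 × 0.6 = 0.36; the unadjusted simulation gave 0.180, 0.299 and 0.364. Rejection at 5% was 23%/56%/74% with visit-level main effects and 5%/6%/6% with symptoms crossed. At zero correlation both were 5 to 6%.

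**Adding the either-score eligibility rule.** 20,000 trials per setting, N = 44, no true ESC effect. Assumed: alpha 0.05, QIDS-PROMIS-A correlation 0.6, visit noise SD 0.5, entry if either Visit 1 score exceeds 0.5 SD. Columns are ESC-symptom correlation/symptom effect.

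| Model | 0.3/0.3 | 0.5/0.4 | 0.6/0.5 |
|---|---|---|---|
| Tertile ESC, no symptoms | 7.1% | 17.6% | 36.8% |
| Tertile ESC, main effects only | 6.9% | 17.0% | 35.4% |
| Tertile ESC, crossed (mean score) | 5.3% | 5.6% | 5.3% |
| Unselected ESC, main effects only | 6.4% | 12.5% | 25.5% |
| Unselected ESC, crossed (mean score) | 5.0% | 5.3% | 5.7% |

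With either quantity zero, main effects only gives 5.0 to 5.1%. Moving the entry cut from 1 SD to 0 takes the last tertile main-effects cell from 30% to 44%. Crossing is not perfect: with noise SD 0.7 at 0.6/0.5 it rejects about 7%, because error in the scores leaves some confounding.

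**Price of crossing.** At correlations 0.3/0.5/0.6, the standard error of tDCS-by-ESC rises by a factor of 1.04/1.14/1.23 (tertile) or 1.03/1.09/1.16 (unselected) with mean scores. For an assumed ESC slope of 0.4, residual SD 1 and no symptom effect, tertile power falls from about 83%/79%/75% to 79%/68%/57%.

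**The case for a change.** The strongest case for amending A2 is that convention does not quite settle it. Classical repeated-measures ANCOVA takes one covariate value per person, whereas A2 speaks of concurrent symptoms and both scales are repeated at each scan. Visit-varying covariates suggest a mixed model, in which crossing is the analyst's choice. A3 examines efficacy by symptoms but is not said to fit them jointly with ESC. One added sentence would cost no data and would remove a choice made after seeing results.

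Part of this stands. The text permits both readings, and main effects alone would adjust almost nothing. The freedom to choose has a small cost: with neither ESC nor symptoms moderating, reporting whichever reading is significant gives about 6 to 8% instead of 5%.

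It does not show that the plan is wrong. Averaging the two scan-visit scores gives one value per person and fits the classical form; crossing the visit-specific scores serves as well. The score type is therefore not an obstacle to the sensible model. The Sample paragraph is also looser support than it seems, since it concerns which trait goes with the abnormal brain patterns, not which trait moderates tDCS; Aim 2 is the better support. A3, though separate, would warn readers if symptoms did moderate the response.

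**Conclusion.** No change is needed. A2 leaves a detail unstated; it does not commit to a faulty model. The method named, the moderation question and the stated purpose all point to symptoms crossed with condition, and on that reading the tDCS-by-ESC test is adjusted for severity, with error rates of about 5 to 6% (about 7% with noisier scores).

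The damaging result needs three things together: a main-effects-only model that the plan does not state, an ESC-symptom correlation, and a symptom effect on the tDCS response. With either of the last two at zero there is no inflation. With both at 0.3 and the eligibility rule applied it is slight (6 to 7%). The 35% figure needs a correlation of 0.6 and an effect of 0.5, which nothing in the documents supports or excludes. All these rates rest on assumed inputs and on the inferred design of one active and one sham visit per person.

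Crossing costs some precision, so neither reading is free. In a 44-person pilot with one-sentence analyses, this is a gap that a competent analyst fills when fitting the model.
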